Protocol Name:	EFFICACY OF TRANEXAMIC ACID IN FOOT AND ANKLE SURGERIES - A RANDOMISED CONTROLLED TRIAL
	Principal Investigator:	[name] [name].
	Primary Contact Name/Contact Info:	[name] MD [contact] [name] MD
	Date Revised:	7/23/2017
	Study Number:	IF# 2089572, GCO#17-04301

HRP-503 PROTOCOL TEMPLATE

- *Note that, depending on the nature of your research, certain questions, directions, or entire sections below may not be applicable. Provide information if and when applicable, and in cases where an entire section is not applicable, indicate this by marking the section “N/A”. Do not delete any sections.*
- ***For any items below that are already described in the sponsor’s protocol, the investigator’s protocol, the grant application, or other source documents, you may simply reference the title and page numbers of these documents in the sections below, rather than cutting and pasting into this document. Do not refer to the Sample Consent document, or information on the application form in this document..***
- *Keep an electronic copy of this version of the document. You will need to modify this copy when making changes.*

Brief Summary of Research (250-400 words):

In foot and ankle surgery, the prevention of postoperative hematoma in a confined space in the wound has a crucial impact on perioperative outcomes. There has been growing emphasis on the role of antifibrinolytics to minimize bleeding and the formation of postoperative hematoma. Approximately 20% of all foot and ankle fractures are open. Excellent operative field without measurable bleeding remain prerequisite of most orthopedic procedures. Increase blood loss can increase the risk of infection, hematoma formation and wound complications. Presence of blood in synovium not only has direct corrosive effects but also causes increased intra capsular pressure leading to capsular fibrosis culminating as ankyloses.

Traditionally, tourniquets are employed to optimize surgical field visualization thereby limiting operative duration and improving technical precision. There are several unwanted effects that can arise from use of tourniquet like neurapraxia, vascular injury, post operative swelling etc. Hence there is a growing interest in achieving the same operative goals without the use of tourniquet.

Antifibrinolytics can be utilized to achieve a blood sparing effect. Its efficacy in reducing intra operative and post operative blood loss is well documented in cardiac surgery, joint replacement surgery, and spine surgery. Tranexamic acid is a synthetic antifibrinolytic drug that competitively blocks the lysine-binding sites of plasminogen, plasmin and tissue plasminogen activator, thereby delaying

	Protocol Name:	EFFICACY OF TRANEXAMIC ACID IN FOOT AND ANKLE SURGERIES - A RANDOMISED CONTROLLED TRIAL
	Principal Investigator:	[name] [name].
	Primary Contact Name/Contact Info:	[name] MD [contact] [name] MD
	Date Revised:	7/23/2017
	Study Number:	IF# 2089572, GCO#17-04301

fibrinolysis and blood clot degradation. It has been effectively used as intravenous (IV), oral, topical, as well as intra articular routes of administration. The effects of IV administration lasts 8-17 hours after the initial dose. Orthopedic surgeons have incorporated TXA into multiple elective surgeries as a means of reducing blood loss and transfusion requirements.

Effectiveness of Tranexamic acid (TXA) in postoperative outcomes is unknown in foot and ankle surgeries. The aim of this study is to evaluate effectiveness of intraoperative doses of intravenous TXA in reducing postoperative bleeding and hematoma formation after foot and ankle surgeries.

1) Objectives

Research Question: Does intraoperative administration of intravenous TXA reduce postoperative bleeding and hematoma formation after foot and ankle surgeries?

Primary outcome: The incidence of wound complications classified as dehiscence, hematoma, necrosis and infection. Wound healing time and length of stay will be evaluated. The first follow up at surgeon's office will be included.

Secondary outcome: The amount of intra operative and post operative blood loss during the first 24 hours in patients undergoing foot and ankle surgeries. Post-operative complete blood count (CBC), duration of surgery and intra operative fluid resuscitation will be recorded. Intraoperative and post operative narcotic consumption.

2) Background

See above. Effectiveness of Tranexamic acid (TXA) is unknown in foot and ankle surgeries. The aim of this study is to evaluate effectiveness of intravenous TXA in reducing post operative blood loss during foot and ankle surgeries.

3) Setting of the Human Research

	Protocol Name:	EFFICACY OF TRANEXAMIC ACID IN FOOT AND ANKLE SURGERIES - A RANDOMISED CONTROLLED TRIAL
	Principal Investigator:	[name] [name].
	Primary Contact Name/Contact Info:	[name] MD [contact] [name] MD
	Date Revised:	7/23/2017
	Study Number:	IF# 2089572, GCO#17-04301

Prospective triple blinded randomized control trial in patients undergoing foot and ankle surgeries. The research study will take place at Mount Sinai West hospital. The site PI is [name], MPH.

4)Resources Available to Conduct the Human Research

For n=200, the feasibility of recruitment is manageable. Recruitment will be done through a coordination of the operating schedule and the surgeon’s office. Patients presenting for preoperative visits at the surgeon’s office or the preoperative joint clinic will be approached. The surgeon will also provide study information (protocol, consent, general information) to patients in the surgeon’s office. After confirmation on the operating schedule, patients will be provided detailed instructions the day before surgery and the final consent will be obtained at the surgeon’s office or joint clinic for patients at Mount Sinai West hospital. On the day of the surgery, the subject will meet the research team in the holding area. The team will finalize participation and ask the subject about the signed consent forms and answer any additional questions. The staff members on this protocol are all employees of Mount Sinai and will either be a resident or attending physicians that are included on the IRB protocol. There are three primary members of the research personnel:

a)[name], MPH – Roles for [name] in this study include serving as primary investigator responsible for study design and planning, data collection, subject recruitment, manuscript writing and preparation, data analysis, safety monitoring, and responding to adverse events and/or complications. He is certified in PPHS/IRB protocols, all Citi/IRB required training in human subject protection, and has prior clinical research experience. He is also a board certified anesthesiologist and assistant professor of anesthesiology with the Icahn School of Medicine and the Mount Sinai Health System.

b) [name] MD – Roles for [name] include serving as primary research coordinator involved in data collection, subject recruitment, manuscript writing and preparation, data analysis, safety monitoring, and responding to adverse events

	Protocol Name:	EFFICACY OF TRANEXAMIC ACID IN FOOT AND ANKLE SURGERIES - A RANDOMISED CONTROLLED TRIAL
	Principal Investigator:	[name] [name].
	Primary Contact Name/Contact Info:	[name] MD [contact] [name] MD
	Date Revised:	7/23/2017
	Study Number:	IF# 2089572, GCO#17-04301

and/or complications. She has completed all of her required CITI training to be IRB certified and has experience in clinical research. In addition she has been a resident physician in anesthesiology with the Icahn School of Medicine in good standing for the previous three years going on her fourth.

c) [name] MD- Roles for [name] in this study include serving as co-investigator responsible for study design and planning, data collection, subject recruitment, manuscript writing and preparation, data analysis, safety monitoring, and responding to adverse events and/or complications. He is certified in PPHS/IRB protocols, all Citi/IRB required training in human subject protection, and has prior clinical research experience. He is also a board certified orthopedic surgeon and assistant professor, department of Orthopedic surgery with the Icahn School of Medicine and the Mount Sinai Health System.

There are institutional processes to ensure that all persons assisting with the protocol will be well informed. The research personnel will conduct regular meetings and department email updates to review the results and safety data of the study. The research personnel will initiate the formation of a safety monitoring board for adverse effects, complications, or complaints from patient subjects.

5) Study Design

Prospective triple blinded randomized control trial. The surgeon will also provide study information (protocol, consent, general information) to patients in the surgeon's office. Recruitment will be done through a coordination of the operating schedule and the surgeon's office. Patients presenting for preoperative visits at the surgeon's office or the preoperative joint clinic will be approached. On the day of the surgery, the subject will meet the research team in the holding area. The team will finalize participation and ask the subject about the signed consent forms and answer any additional questions. All patients will be provided with copies of the IRB protocol and consent if they wish to have it. Copy of the consent form will be sent in a secured email to the potential subject. The email will be secured by

	Protocol Name:	EFFICACY OF TRANEXAMIC ACID IN FOOT AND ANKLE SURGERIES - A RANDOMISED CONTROLLED TRIAL
	Principal Investigator:	[name] [name].
	Primary Contact Name/Contact Info:	[name] MD [contact] [name] MD
	Date Revised:	7/23/2017
	Study Number:	IF# 2089572, GCO#17-04301

entering in [SECURE] in the e-mail subject line. Once recruited blinding assessments will be done by the study team.

Patients will be assigned randomly using a computer- generated table of numbers to either TXA group (Tranexamic acid group) or placebo (saline group). Patients assigned to TXA group will receive 10mg/kg IV TXA in a 100cc normal saline bag at the time of induction and a second dose prior to skin closure. Patients in the placebo group will receive 100cc normal saline IV at the time of induction and a second dose prior to skin closure. Otherwise, the patient, surgeon, and anesthesiologist in the case will be blinded.

a) Recruitment methods: Patients will be recruited and consented at the surgeons office or pre-operative testing/Joint clinic.

b) Inclusion and Exclusion Criteria

Inclusion criteria: ASA (American Society of Anesthesiology) class I-IV, age 18-75.

Exclusion criteria: ASA class V, patient refusal, patients with known coagulopathy disorder, renal insufficiency, hepatic dysfunction, serious cardiac disease, patients receiving antiplatelet and/or anticoagulant drugs, or an allergy to TXA or will be excluded.

c)Number of Subjects

We intend to recruit 200 patients.

Based on a confidence level of 99% with a Z score of 2.58, standard deviation of .5 and a confidence interval of 10% our sample size should be 166. For ease of statistical calculations we rounded up to 200 patients. Literature search reveals only one previous study where TXA has been used in calcaneal fractures. Xie et al concluded in a study with 90 patients that TXA reduces post operative blood loss. We intend to use a higher sample size to see any statistical significance.

	Protocol Name:	EFFICACY OF TRANEXAMIC ACID IN FOOT AND ANKLE SURGERIES - A RANDOMISED CONTROLLED TRIAL
	Principal Investigator:	[name] [name].
	Primary Contact Name/Contact Info:	[name] MD [contact] [name] MD
	Date Revised:	7/23/2017
	Study Number:	IF# 2089572, GCO#17-04301

$$Z^2 * (p) * (1-p)$$

$$SS = \frac{\quad}{c^2}$$

Where:

Z = Z value (2.58 for 99% confidence level)
p = percentage picking a choice, expressed as decimal (.5 used for sample size needed)
c = confidence interval, expressed as decimal (e.g., .01= ±1)

Sample size= [(2.58²)(.5)(.5)]/(.1²)=166 subjects
For effect size, we expect a Cos d medium effect of 0.5.

Intergroup comparisons will be performed using the Mann-Whitney U test. Qualitative data will be compared using the chi-square test or Fisher’s exact test. Only p < .05 will be considered statistically significant.

d)Study Timelines

2018-2019 and subsequent data analysis. The subject’s participation will be from time of enrollment in the pre-operative period until first postoperative day. The first follow up visit at the surgeons office will be included as well. Estimated date of enrollment completion will be when 200 eligible subjects are enrolled in final data analysis. Estimate date for study completion will be June 2018.

	Protocol Name:	EFFICACY OF TRANEXAMIC ACID IN FOOT AND ANKLE SURGERIES - A RANDOMISED CONTROLLED TRIAL
	Principal Investigator:	[name] [name].
	Primary Contact Name/Contact Info:	[name] MD [contact] [name] MD
	Date Revised:	7/23/2017
	Study Number:	IF# 2089572, GCO#17-04301

e)Endpoints

Conclusion of data analysis and evaluation of significance of findings, as measured by primary and secondary outcomes listed under Objectives (item #1) for purposes of quality improvement.

f)Procedures Involved in the Human Research

Prospective randomized controlled trial and data analysis only. TXA group and placebo group. Intraoperative care of the patient will be provided by an anesthesia team member who is a part of the Mount Sinai System. The anesthesia provider will not be aware of the randomization of the patient. Standard post-operative orders will be written for patients during their time in the PACU.

g)Specimen Banking

N/A

h)Data Management and Confidentiality

Data collected in excel file to be de-identified after initial collection. Excel file be subsequently encrypted and shared only between the above listed investigators via secure Mt. Sinai (chpnet) electronic mail.

The information included in the data will be medical record number, age, gender, ASA class, type of surgery, duration of surgery, the amount of intra operative and post operative blood loss during the first 24 hours in patients will be collected. Wound complications (eg dehiscence, hematoma, necrosis and infection), wound healing time and length of stay will be evaluated. Post operative complete blood count will be recorded. The first follow up at surgeon’s office will be the other data collected.

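### Tourniquet use is neither fixed nor recorded in the supplied text; if practice is mixed, the unstratified Mann-Whitney test of intraoperative blood loss stays unbiased but loses power

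*Combined protocol and SAP*

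**What the plan says.** The Brief Summary of Research gives a paragraph to the tourniquet: "Traditionally, tourniquets are employed to optimize surgical field visualization thereby limiting operative duration and improving technical precision". It then lists harms and concludes: "Hence there is a growing interest in achieving the same operative goals without the use of tourniquet". Antifibrinolytics follow as a means of sparing blood.

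Section 1 (Objectives) makes wound complications primary: "The incidence of wound complications classified as dehiscence, hematoma, necrosis and infection". Blood loss is secondary: "The amount of intra operative and post operative blood loss during the first 24 hours in patients undergoing foot and ankle surgeries". The same section adds "Post-operative complete blood count (CBC), duration of surgery and intra operative fluid resuscitation will be recorded".

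Section 5h (Data Management and Confidentiality) lists the data items, beginning "The information included in the data will be medical record number, age, gender, ASA class, type of surgery, duration of surgery", followed by blood loss, wound outcomes, blood count and the follow-up visit. No tourniquet item appears there, nor in eligibility (5b), allocation (5, Study Design) or procedures (5f).

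The analysis text in section 5c says "Intergroup comparisons will be performed using the Mann-Whitney U test", with chi-square or Fisher's exact tests for qualitative data. It mentions no stratification or covariate adjustment.

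**The concern.** A tourniquet is used to control bleeding in the surgical field, so it is likely to be a strong determinant of intraoperative loss. The protocol itself calls it traditional, and nothing in the supplied text makes its use uniform. If some cases have one and some do not, the pooled ranks carry the difference between the two kinds of case as noise, and a real drug effect becomes harder to detect.

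Interpretation also suffers. With no tourniquet record, a null result for intraoperative loss could mean no effect, or an effect obscured by the mix of cases. Type and duration of surgery are collected, but they do not show whether a tourniquet was inflated.

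**Working it through.** **The plan's own figure.** Section 5c: 2.58² × 0.5 × 0.5 / 0.1² = 166.4, which matches the stated 166 (then rounded up to 200). This is a precision formula for a single proportion and says nothing about power for blood loss.

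**Baseline with homogeneous cases.** Inputs from the documents: 200 patients, p < .05, effect size 0.5. Assumed: 1:1 allocation (100 per arm), a two-sided test, and 0.5 read as Cohen's d.
- Normal approximation: 0.5 × √(100/2) = 3.54; 3.54 − 1.96 = 1.58; power 94%.
- Mann-Whitney, with efficiency 3/π: 0.5 × √(95.5/2) = 3.45; 3.45 − 1.96 = 1.49; power 93%.

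**Mixed practice.** The documents give no tourniquet share, no ratio of losses and no spread, so all three are assumptions. Take log-normal loss with within-stratum log-SD 0.6, a drug shift of 0.5 × 0.6 = 0.30 in every case, and tourniquet cases losing k times less blood. With tourniquet share f, the pooled SD is √(0.36 + f(1 − f)(ln k)²).

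Hand check at f = 50%:

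| k | Pooled SD | Shift / pooled SD | Approximate power |
|---|---|---|---|
| 2 | 0.693 | 0.433 | 86% |
| 3 | 0.813 | 0.369 | 74% |
| 5 | 1.004 | 0.299 | 56% |

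The last column is Φ(shift/SD × √50 − 1.96). Simulation of the actual rank tests (3,000 runs) gives somewhat lower pooled power:

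| Tourniquet share | Pooled Mann-Whitney, k = 2 to 5 | Stratified (van Elteren) |
|---|---|---|
| 50% | 83%, 68%, 51% (k = 2, 3, 5) | 92–93% |
| 25% | about 86% to 66% | about 93% |
| 10% or 90% | about 91% to 83% | about 93% |
| 0% or 100% | no loss | no cost |

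**Sensitivity.**
- Wider spread (log-SD 1.0, 50% share): pooled 89%, 84%, 74% against 92–93% stratified.
- A second simulation (4,000 runs), with tourniquet cases 2 SD lower: pooled 74%, 66%, 75% at shares of 25%, 50%, 75%; stratified 93% throughout. On the log-SD 0.6 scale, 2 SD is a ratio of e^1.2 = 3.3, so this agrees with the k = 3 row.
- Drug acts only without a tourniquet (50% share, k = 2, 3, 5): pooled 34%, 24%, 18%; stratified 38–40%.
- No drug effect: pooled rejection rate 4.5–5.4%, so type I error is held.
- Effect of 0.5 defined on the overall SD (50% share): pooled power 93%, 92%, 91%.

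**The case against.** The strongest reply is that the mixing is assumed. This is one hospital, and the research team described in section 4 includes one orthopaedic surgeon, so practice may be uniform. If all cases or none use a tourniquet, nothing is lost. That stands: the documents leave mixed practice open but do not establish it.

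Second, the size depends on scale. The protocol's 0.5 is unqualified. Read against the SD of all enrolled patients, the pooled test keeps its expected power. That also stands. A 50% share is moreover the least favourable case for the variance added by mixing.

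Third, the affected quantity is peripheral. A reader might infer from the background that operating without a tourniquet is what the trial is for. The research question and the aim are instead about bleeding and haematoma after surgery, and no objective mentions tourniquet-free operating. The modelled loss concerns only the intraoperative part of a secondary outcome.

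Fourth, a reader might infer bias, or a loss that can never be repaired. Neither is supported. Randomisation balances tourniquet use in expectation, and type I error stays near 5%. Actual use might be retrieved later from operative records, since medical record numbers are collected, although de-identification after collection makes this harder. What could not be reliably recovered is the plan as it stood before allocation.

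None of this removes the point that recording the variable is cheap and that stratifying costs no measurable power when practice is uniform.

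**Conclusion.** The point holds as a low-cost improvement to one secondary comparison, conditional on mixed tourniquet practice. Within the assumptions shown (100 per arm, log-SD 0.6, within-stratum shift 0.5 SD, ratio 2 to 5), pooled power ranges from about 91% down to 51% depending on share and ratio, against about 93% stratified. The loss is smaller if blood loss is more variable, and nil if practice is uniform. If 0.5 was meant on the overall SD, there is no shortfall against expected power, only efficiency left unused.

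The figures say nothing about wound complications, the primary outcome, and they do not indicate a risk of false positives. Absence of any tourniquet item is established only for the text that was available; a mention between sections 5h and 5j cannot be excluded.

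**What to change.** Add three items to the data list in section 5h: tourniquet planned (yes/no), recorded before randomisation; tourniquet used (yes/no); and inflation minutes.

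In section 5c, specify that intraoperative blood loss is compared by a van Elteren test (the stratified Mann-Whitney) with planned tourniquet use as the stratum, and that descriptive results are shown by stratum. With a single stratum this reduces to the ordinary Mann-Whitney test, so it can be prespecified without knowing whether practice will vary. Use the planned value, because actual use comes after the first dose at induction and could be influenced by bleeding.

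The cost is three fields and a stratified form of a test already planned. The small downside is that the surgeon must state the plan before allocation. The change recovers little power if the drug acts only without a tourniquet (38–40% stratified in the scenario above), which is why the results by stratum should be shown. It does not touch the primary outcome and takes no position on whether a tourniquet should be used.

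### The CBC is planned as a post-operative value only, which leaves a cheap gain in precision unused on a secondary outcome

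*Combined protocol and SAP*

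**What the plan says.** Section 1 (Objectives) places the CBC under the secondary outcome: "Post-operative complete blood count (CBC), duration of surgery and intra operative fluid resuscitation will be recorded". Section 5h (Data Management and Confidentiality) repeats it: "Post operative complete blood count will be recorded". Neither place mentions a pre-operative CBC, hemoglobin or hematocrit, and neither says which CBC component is meant or when it is drawn.

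The analysis text, at the end of section 5c, is general: "Intergroup comparisons will be performed using the Mann-Whitney U test". Chi-square or Fisher's exact tests are for qualitative data. No covariate and no change from baseline is mentioned. The significance rule is "Only p < .05 will be considered statistically significant".

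No sentence says outright that the CBC is compared between arms. That follows from its place under the secondary outcome, from section 5e, which evaluates significance "as measured by primary and secondary outcomes listed under Objectives (item #1"), and from the Mann-Whitney sentence.

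Blood loss is also a secondary outcome in its own right: "The amount of intra operative and post operative blood loss during the first 24 hours in patients undergoing foot and ankle surgeries". No method of measuring it is given.

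**The concern.** A single post-operative hemoglobin combines where the patient started with what was lost. Eligibility is broad (ASA I-IV, age 18-75, no single procedure), so starting values can be expected to differ between patients. Without the pre-operative value, neither a fall nor a baseline-adjusted difference can be computed, and the spread in starting values stays in the error term.

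At stake is the precision of the one laboratory measure that bears on the bleeding question. If the trial shows no clear CBC difference, part of the reason may be noise that one chart value per patient could have removed.

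**Working it through.** **Inputs from the protocol.** Total N: "We intend to recruit 200 patients". Alpha 0.05. A medium standardized effect of 0.5 is stated in section 5c, but it is attached to no outcome and does not enter the sample-size formula.

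**Assumptions.** Allocation 1:1, so n = 100 per arm (ratio not stated). Two-sided test (not stated). Pre/post correlation r of 0.3 to 0.8 (not in the documents). A 0.3 SD difference as an illustration of a smaller effect.

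**The plan's own figure.** Z²p(1−p)/c² = 2.58² × 0.5 × 0.5 / 0.1² = 166.41, which reproduces the stated 166 before rounding up to 200. It is a precision formula for one proportion and says nothing about power for the CBC.

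**Formulas**, in SD units of the post-operative value:
- Post-operative value alone: SE = √(2/n) = √(2/100) = 0.1414.
- ANCOVA on the pre-operative value: error variance is multiplied by (1 − r²), so SE = 0.1414 × √(1 − r²).
- Simple change score: error variance is multiplied by 2(1 − r).
- Power = Φ(δ/SE − 1.96).

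**Worked case, δ = 0.3.** Unadjusted: 0.3/0.1414 = 2.121; 2.121 − 1.960 = 0.161; power 56%. At r = 0.7: SE = 0.1414 × √0.51 = 0.1010; 0.3/0.1010 = 2.970; 2.970 − 1.960 = 1.010; power 84%.

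| r | Variance, ANCOVA | Variance, change score | Equivalent unadjusted n per arm, 100/(1 − r²) | Power, 0.3 SD | Power, 0.5 SD |
|---|---|---|---|---|---|
| Post-operative only | 1.00 | – | 100 | 56% | 94% |
| 0.3 | 0.91 | 1.40 | 110 | 60% | 96% |
| 0.5 | 0.75 | 1.00 | 133 | 69% | 98% |
| 0.7 | 0.51 | 0.60 | 196 | 84% | >99% |
| 0.8 | 0.36 | 0.40 | 278 | 94% | >99% |

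The two power columns are for ANCOVA, apart from the first row. For the Mann-Whitney test itself, with asymptotic relative efficiency 0.955 (effective n = 95.5 per arm), the unadjusted figures are about 55% and 93%.

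**Change score.** Its variance falls below that of the post-operative value alone only when r exceeds 0.5. ANCOVA gains at any non-zero r.

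**Missing baselines.** If a fraction m of baselines is missing at random and filled with the overall mean, the covariate's variance and its covariance with the outcome both shrink by (1 − m). The reduction in error variance is then about (1 − m)²r²/(1 − m) = (1 − m)r².

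**The case against.** The strongest reply is that little depends on this. The CBC sits under a secondary outcome, the primary outcome is wound complications, and blood loss is also recorded as an amount. The 0.3 SD difference is a reviewer's illustration; at the only effect size in the protocol, 0.5, unadjusted power is already about 94%. All of that stands and limits the weight of the point. The reassurance from 0.5 is itself limited, since nothing links that figure to hemoglobin.

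The evidence of absence is also imperfect. The 5h list omits fluids and narcotic use, both named in section 1, so it is not exhaustive, and the text between sections 5h and 5j was not available to this review. Still, section 1 also specifies only the post-operative value.

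A reader might go further in four ways that the documents do not support:
- *That the comparison is biased by baseline imbalance.* Randomization makes it unbiased in expectation, and its standard error already allows for chance imbalance.
- *That post-operative hemoglobin mostly reflects the starting value.* That needs r² > 0.5, so r above about 0.71, and the documents give no r.
- *That every patient already has a pre-operative CBC, so no new draw is needed.* Section 5a says "Patients will be recruited and consented at the surgeons office or pre-operative testing/Joint clinic": some may attend only the office, and nothing says that a CBC is drawn at any of these places.
- *That a paired hemoglobin change is the best check on the recorded blood loss.* Hemoglobin also responds to dilution, and intra-operative fluid appears in the same sentence as the CBC.

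**Conclusion.** The point holds as one of efficiency. As written, the CBC is post-operative only and the stated test is unadjusted, so variation in starting hemoglobin is left in the comparison. Adjustment would remove 9% of the error variance at r = 0.3 and 64% at r = 0.8. For a 0.3 SD difference, power would rise from 56% to between 60% and 94%; for 0.5 SD the gain is only a few percentage points.

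These sizes rest on an assumed r, 1:1 allocation, a two-sided test and complete baselines. That the CBC is compared between arms at all is inferred. No primary conclusion depends on the point and the planned comparison is not invalid, but the improvement is cheap enough to be worth making.

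**What to change.** 1. Add the last pre-operative hemoglobin, taken from the chart where available, to section 1 and to the 5h data list. Extract it with the other data, because 5h de-identifies the file after initial collection and later linkage may be difficult.
2. Name hemoglobin as the CBC measure, at one fixed post-operative time point. Without that, the adjusted outcome is still undefined.
3. In place of the plain Mann-Whitney test for this outcome, prespecify ANCOVA of post-operative hemoglobin on arm and pre-operative hemoglobin (rank ANCOVA if skewed). Report the adjusted difference with a 95% CI. Do not rely on a simple change score, which loses precision if r is below 0.5.
4. Fill a missing baseline with the overall baseline mean, so that no patient is dropped. This is acceptable because baseline is independent of randomized arm.

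The cost is one extracted value per patient and one model. The documents do not say how many patients have a pre-operative CBC. The gain shrinks roughly in proportion to the share missing, so that if half are missing, about half of the variance reduction is lost.

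### Narcotic consumption is compared by an unstratified Mann-Whitney test, and nerve block and anesthetic technique are neither fixed nor listed for recording, so the comparison can lose power if block use is mixed

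*Combined protocol and SAP*

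**What the plan says.** - **Outcome.** Section 1 ends its list of secondary outcomes with "Intraoperative and post operative narcotic consumption". It gives no unit, conversion between drugs or time window; the 24-hour period there belongs to blood loss.
- **Test.** Section 5c: "Intergroup comparisons will be performed using the Mann-Whitney U test". Categorical data get a chi-square or Fisher test, and "Only p < .05 will be considered statistically significant". No stratified or adjusted analysis is mentioned.
- **Size and allocation.** Section 5c: "We intend to recruit 200 patients". Section 5 describes a computer-generated random list with no stratification factor.
- **Anesthetic care.** Section 5f assigns intraoperative care to a member of the hospital system's anesthesia staff, blinded to allocation. For recovery, "Standard post-operative orders will be written for patients during their time in the PACU". Neither sentence specifies a technique, a block or an opioid regimen. Section 10 refers to a usual anesthetic regimen, but only to explain billing, and does not define it.
- **Data.** Section 5h begins: "The information included in the data will be medical record number, age, gender, ASA class, type of surgery, duration of surgery". It goes on to blood loss, wound outcomes, length of stay, blood count and the first office visit. Nerve block, anesthetic technique and narcotic consumption are not in the list.

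**The concern.** In foot and ankle surgery, a nerve block or regional technique is likely to change intraoperative and early postoperative narcotic use considerably, whichever arm the patient is in. If some patients have a block and others do not, a pooled rank test counts that spread as noise. A test that ranks patients within block strata removes it, but only if block status has been recorded.

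Three things coincide here: the technique is not fixed, it is not among the listed data, and the only planned test has no strata. At stake is the precision of one secondary comparison, together with the ability to see whether block use happened to differ between arms. With 100 per arm and a 50% block share, the chance difference in block share has a standard deviation of √(2 × 0.25/100) = 0.071, about 7 percentage points.

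The missing narcotic field is a separate mismatch between sections 1 and 5h, and needs no assumption to see.

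**Working it through.** **The plan's own figures.** Section 5c gives "Sample size= [(2.58²)(.5)(.5)]/(.1²)=166 subjects". Check: 2.58² × 0.25 / 0.01 = 166.4, so it reproduces. It is a precision formula for one proportion and says nothing about narcotic use. Section 5c adds "For effect size, we expect a Cos d medium effect of 0.5", without naming the outcome or the SD. With 100 per arm (equal allocation assumed), two-sided 5% (sidedness assumed) and Mann-Whitney efficiency 0.955, power is Φ(d√(95.5/2) − 1.96) = Φ(0.5 × 6.910 − 1.96) = Φ(1.495) = 93%.

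**Inputs assumed because the documents give none.** Narcotic use is log-normal with within-stratum log-SD 0.7. TXA lowers it by 25%. A block lowers it by 40%, 60% or 75%. The block share q is 10%, 50% or 90%.

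**Formulas.**
- TXA effect in within-stratum SDs: d = −ln(0.75)/0.7 = 0.288/0.7 = 0.411.
- Block effect in within-stratum SDs: B = −ln(1 − reduction)/0.7.
- Pooled SD: √(1 + q(1 − q)B²). Pooled standardised effect: d divided by this.
- Stratified power: Φ(0.411 × 6.910 − 1.96) = Φ(0.880) = 81%.

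| Block share | Block lowers use by | B | Pooled SD | Pooled effect | Pooled power | Loss against 81% |
|---|---|---|---|---|---|---|
| 10% or 90% | 40% | 0.730 | 1.024 | 0.401 | 79% | 2 points |
| 10% or 90% | 60% | 1.309 | 1.074 | 0.383 | 75% | 6 points |
| 50% | 40% | 0.730 | 1.064 | 0.386 | 76% | 5 points |
| 50% | 60% | 1.309 | 1.195 | 0.344 | 66% | 15 points |
| 50% | 75% | 1.980 | 1.407 | 0.292 | 52% | 29 points |

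**Simulation of the same model, pooled Mann-Whitney against van Elteren.**
- 50% share, over repeated runs: 74-76% against 79-81% (block −40%), 63-66% against 80-81% (−60%), 48-51% against 79-82% (−75%).
- Block −60%: 77% against 82% at a 10% share, and 76% against 80% at 90%. With block −40%, the loss at these shares is 1-2 points.
- Block −75% at a 20% or 80% share: 63% against 81%.
- With 3,000 trials, the standard error of a power near 65% is √(0.65 × 0.35/3000) = 0.9 points, which accounts for most of the spread between runs.
- With no TXA effect, both tests reject about 5% of the time.

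**Sensitivity at a 50% share and block −60%.**
- Log-SD 1.0: 43% against 51%. Log-SD 1.3: 30% against 33%.
- TXA effect 10% instead of 25%: 14% against 19%.
- Stratum defined by planned block, with 90% agreement between plan and delivery: 66% against 76%, a gain of 10 points.

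**The case against.** **The size is assumed.** Every input that drives the loss comes from outside the documents, and a 50% share is the one that adds most variance. If nearly all patients have a block, or nearly none, little is lost. This stands, and is why the result is given as a range.

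**The plan's 0.5 may already allow for it.** If 0.5 is measured against the total SD, block variation is inside it and power stays near 93%. The documents do not say which SD is meant, so this reading can be neither excluded nor relied on.

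**Stratifying does not rescue a weak comparison.** With a larger SD or a smaller TXA effect, both tests have low power. This stands; the gain is then only a few points.

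**The 5h list may not be exhaustive.** It also leaves out intraoperative fluids, which section 1 says will be recorded, so absence from 5h is not proof that an item will go uncollected. Medical record number is kept at first, so retrieval from the anesthesia record might be possible, although de-identification could end that. The text between the 5h list and section 5j was not available to this review. What remains is that the reviewed text makes no provision for block or technique.

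**Stronger readings that the documents do not support.** A reader might infer that block use will swamp any TXA effect; that holds only for heavy mixing with a very strong block effect. A reader might infer bias or a false-positive problem; random assignment rules out both. A reader might call a null result uninterpretable; it would be a valid but less precise result under usual care. Nor do the documents say that several narcotics will be used. A common unit is needed if they are.

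**Conclusion.** The point holds as a question of efficiency and data capture. The planned comparison of narcotic consumption is valid, but it takes no account of a likely strong determinant that the plan neither fixes nor lists for recording.

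Under the assumptions above (100 per arm, log-SD 0.7, TXA effect 25%), the loss against a stratified test is about 1-6 points at a 10% or 90% block share and about 5-17 points at a 50% share, for block effects of 40-60%. Among the cases run, about 30 points is reached only at a 50% share with a 75% block effect. The loss is smaller if the SD is larger, and the gain from the fix is smaller if the planned block often differs from the one given.

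The absence of narcotic consumption from the 5h list stands without any assumption. Since the outcome is secondary, with no bias or type I error problem, the change is one to consider.

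**What to change.** **Section 5h.** Add the anesthetic technique and nerve block planned before the first study dose; block yes/no is enough for the stratum. Add each narcotic given, with dose and time, so that amounts can be put on a common unit and summed over a stated period.

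**Section 5c.** Replace the pooled Mann-Whitney for this outcome with a sentence such as: narcotic consumption will be compared between arms with a van Elteren (stratified Wilcoxon) test, stratified by whether a nerve block was planned before the first study dose. Using the plan rather than the block delivered means that treatment cannot affect the stratum.

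If block use turns out to be almost uniform, the stratified test behaves much like the planned one, so little is given up.

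**Cost.** Slight abstraction work from the anesthesia record and one sentence of analysis text. Anesthetic care does not change. The fields should be in place before enrollment, since planned block may not be recoverable afterwards.
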